10.1.3.1 Baseline Assessments in irRECIST

In irRECIST, baseline assessment and measurement of measurable/non-measurable and target/non-target lesions and lymph nodes are in line with RECIST 1.1

10.1.3.2 Follow-up Assessments in irRECIST

A. Follow-up recording of target and new measurable lesions

A key difference in irRECIST is that the appearance new lesions does not automatically indicate progression. Instead, all measured lesions (baseline-selected target lesions and new measurable lesions) are combined into the total measured tumor burden (TMTB) at follow up. Baseline-selected target lesions and new measurable lesions are NOT assessed separately. Measurements of those lesions are combined into the TMTB, and one combined assessment provided.

In order to be selected as new measurable lesions (≤ 2 lesions per organ, ≤ 5 lesions total,

per time point), new lesions must meet criteria as defined for baseline target lesion selection and meet the same minimum size requirements of 10 mm in long diameter and minimum 15 mm in short axis for new measurable lymph nodes. New measurable lesions should be prioritized according to size, and the largest lesions elected as new measured lesions.

B. Follow-up non-target assessment

RECIST 1.1 definitions for assessment of non-target lesions apply. The response of non-target lesions primarily contributes to the overall response assessments of irCR and irNon-CR/Non-PD (irNN). Non-target lesions do not affect irPR and irSD assessments. Only a massive and unequivocal worsening of non-target lesions alone, even without progress in the TMTB is indicative of irPD. In alignment with RECIST 1.1, baseline selected non-target lesions can never convert to measurable lesions, not even if they increase in size at subsequent time points and become measurable. Only true new lesions can be measured and contribute to the TMTB.

C. Follow-up for New Non-Measurable Lesions

All new lesions not selected as new measurable lesions are considered new non-measurable lesions and are followed qualitatively. Only a massive and unequivocal progression of new non-measurable lesions leads to an overall assessment of irPD for the time point. Persisting new non-measurable lesions prevent irCR.

10.1.3.3 Overall Assessments for irRECIST

The irRECIST overall tumor assessment is based on TMTB of measured target and new lesions, non-target lesion assessment and new non-measurable lesions. At baseline, the sum of the longest diameters (SumD) of all target lesions (up to 2 lesions per organ, up to total 5 lesions) is measured. At each subsequent tumor assessment (TA), the SumD of the target lesions and of new, measurable lesions (up to 2 new lesions per organ, total 5 new lesions) are added together to provide the total measurable tumor burden (TMTB).

Overall Assessments by irRECIST	
Complete Response (irCR)	Complete disappearance of all measurable and non-measurable lesions. Lymph nodes must decrease to < 10 mm in short axis.
Partial Response (irPR)	Decrease of $\geq 30\%$ in TMTB relative to baseline, non-target lesions are irNN, and no unequivocal progression of new non-measurable lesions 
 • If new measurable lesions appear in subjects with no target lesions at baseline, irPD will be assessed. That irPD time point will be considered a new

	
baseline, and all subsequent time points will be compared to it for response assessment. irPR is possible if the TMTB of new measurable lesions decreases by $\geq 30\%$ compared to the first irPD documentation
 
 • irRECIST can be used in the adjuvant setting, in subjects with no visible disease on CT/MRI scans. The appearance of new measurable lesion(s) automatically leads to an increase in TMTB by 100% and leads to irPD. These subjects can achieve a response if the TMTB decreases at follow-up, as a sign of delayed response. • Based on the above, sponsors may consider enrolling subjects with no measurable disease and/or no visible disease in studies with response related endpoints.
Stable Disease (irSD)	Failure to meet criteria for irCR or irPR in the absence of irPD
Progressive Disease (irPD)	
Minimum 20% increase and minimum 5 mm absolute increase in TMTB compared to nadir, or irPD for non-target or new non-measurable lesions. Confirmation of progression is recommended minimum 4 weeks after the first irPD assessment. An irPD confirmation scan may be recommended for subjects with a minimal TMTB %-increase over 20% and especially during the flare time-window of the first 12 weeks of treatment, depending on the compound efficacy expectations, to account for expected delayed response.
 
 • In irRECIST a substantial and unequivocal increase of non-target lesions is indicative of progression. • IrPD may be assigned for a subject with multiple new non-measurable lesions if they are considered to be a sign of unequivocal massive worsening
Other	
irNE: used in exceptional cases where insufficient data exist.
 
irND: in adjuvant setting when no disease is detected
 
irNN: no target disease was identified at baseline, and at follow-up the subject

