3. PARTICIPANT SELECTION AND ENROLLMENT PROCEDURES

3.1 Inclusion Criteria

- 3.1.1 Histologically confirmed metastatic or locally advanced Merkel Cell Carcinoma (includes in-transit or bilateral bulky disease) with at least two distinct sites of disease.
- 3.1.2 Subjects with brain metastases and/or carcinomatous meningitis are eligible providing they are neurologically stable (if systemic steroids are required, subjects should be stable on the lowest clinically effective dose, as steroids may interfere with the activity of immunotherapy if administered at the time of the first Anti-PD-1/PD-L1 dose.)
- 3.1.3 Must be at least 14 days since treatment for MCC, and recovered (baseline or residual non ir Grade 1 toxicity or ir Grade 2 toxicity at the investigator's discretion, see section 4.1.1) from any clinically significant toxicity experienced during treatment before the first dose of on study pembrolizumab therapy.
- 3.1.4 Eastern Cooperative Oncology Group (ECOG) performance status of 0 to 2.
- 3.1.5 Life expectancy of ≥ 16 weeks.
- 3.1.6 Subjects must have measurable disease according to RECIST v1.1, and have baseline (screening/baseline) radiographic images, (e.g. CT, PET CT or MRI brain, chest, abdomen, pelvis, to be determined by the attending physician) within 4 weeks of confirmation of eligibility and within 6 weeks before the initiation of on study pembrolizumab therapy.
- 3.1.7 Required values for initial laboratory tests:
 - WBC: $\geq 2000/\mu\text{L}$ ($\sim 2 \times 10^9/\text{L}$)
 - ANC: $\geq 1000/\mu\text{L}$ ($\sim 1 \times 10^9/\text{L}$)
 - Platelets: $\geq 50 \times 10^3/\mu\text{L}$ ($\sim 50 \times 10^9/\text{L}$)
 - Hemoglobin: ≥ 8 g/dL
 - Calculated creatinine clearance (eGFR) greater than 30mL/min
 - AST/ALT: Less than 2.5 x ULN for subjects without liver metastasis, less than 5 times ULN for liver metastases
 - Bilirubin: less than 3.0 x ULN (except for subjects with Gilbert's Syndrome, who must have a total bilirubin of less than 3.0 mg/dL)
 - Non-clinically significant laboratory abnormalities such as lipase elevation would not be an exclusion.
- 3.1.8 No known active or chronic infection with HIV, Hepatitis B, or Hepatitis C, or active infection requiring systemic antibiotics. Testing for the above is not required unless clinically suspected.

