Target lesions: All measurable lesions up to a maximum of 2 lesions per organ and 5 lesions in total, representative of all involved organs, should be identified as **target lesions** and recorded and measured at baseline. Target lesions should be selected on the basis of their size (lesions with the longest diameter), be representative of all involved organs, but in addition should be those that lend themselves to reproducible repeated measurements. It may be the case that, on occasion, the largest lesion does not lend itself to reproducible measurement in which circumstance the next largest lesion which can be measured reproducibly should be selected. A sum of the diameters (longest for non-nodal lesions, short axis for nodal lesions) for all target lesions will be calculated and reported as the baseline sum diameters. If lymph nodes are to be included in the sum, then only the short axis is added into the sum. The baseline sum diameters will be used as reference to further characterize any objective tumor regression in the measurable dimension of the disease.

Non-target lesions. All other lesions (or sites of disease) including any non-measurable as well as measurable lesions over and above the 5 target lesions should be identified as non-target lesions and should also be recorded at baseline. Measurements of these lesions are not required, but the presence, absence, or in rare cases unequivocal progression of each should be noted throughout follow-up.

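### Section 10.1.3.3 conflicts with the other response criteria on non-target lesions and on nodal measurement, so one scan can be irPR or irSD depending on the sentence followed

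*Combined protocol and SAP*

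**What the plan says.** **Non-target lesions.** The irPR row of the table in Section 10.1.3.3 requires a decrease of at least 30% "in TMTB relative to baseline, non-target lesions are irNN, and no unequivocal progression of new non-measurable lesions". Section 10.1.3.2, part B, states "Non-target lesions do not affect irPR and irSD assessments", apart from massive worsening, which makes irPD. irSD is the residual category: anyone who is not irCR, irPR or irPD.

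**irNN.** Section 10.1.3.2, part B, uses the label as shorthand for Non-CR/Non-PD. Section 10.1.2.3 defines that status as at least one non-target lesion persisting. The last row of the table in 10.1.3.3 gives a different meaning: "irNN: no target disease was identified at baseline". Criterion 3.1.6 says "Subjects must have measurable disease according to RECIST v1.1".

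**Nodes.** Section 10.1.3.3 says "At baseline, the sum of the longest diameters (SumD) of all target lesions" is measured. It then carries SumD into TMTB at each later assessment, with no exception for nodes. Section 10.1.2.1 says "A sum of the diameters (longest for non-nodal lesions, short axis for nodal lesions) for all target lesions will be calculated", and allows only the short axis for nodes at baseline and follow-up. Section 10.1.3.1 says that in irRECIST "measurement of measurable/non-measurable and target/non-target lesions and lymph nodes are in line with RECIST 1.1". The irCR row and the size rule for new nodes also use the short axis.

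**The concern.** irPR and irSD are named in the primary objective (1.1), the secondary objective (1.2) and the outcome measure (Section 10). Response rate and duration of response are secondary endpoints (12.4). If two sentences of the plan give different categories for one scan, the irRECIST results depend on which sentence the assessor followed. The non-target condition also runs the wrong way: taken at its word, clearing all non-target disease costs the patient the irPR category. For nodes, the axis used could separate a RECIST category from an irRECIST category with no immune-related pattern behind the difference.

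**Working it through.** The plan states no figure on this point, so there is none to reproduce. The check is a comparison of rules, followed by percentage changes on assumed lesion sizes.

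**1. Non-target condition.** Take irNN in its attainable sense, Non-CR/Non-PD. Every patient below has TMTB down by 30% or more and no progression anywhere.

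| Target disease | Non-target disease | irPR row, 10.1.3.3 | Sentence in 10.1.3.2 B |
|---|---|---|---|
| Residual | Persists | irPR | irPR |
| Residual | All gone | irSD | irPR |
| Residual | None at baseline | irSD if read literally; irPR if the condition is treated as not applicable | irPR |
| All gone | All gone, no new lesions | irCR | irCR |

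The second row is the clear conflict and the third depends on the reading. Absence of non-target disease is possible: criterion 3.1.1 asks for only two distinct sites, and Section 10.1.2.1 makes all measurable lesions targets, up to 2 per organ and 5 in total.

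**2. Nodal axis.** Change = (follow-up sum - baseline sum) / baseline sum. The irPR size threshold is a fall of at least 30%. All sizes are assumptions, in mm, with nodes given as longest diameter x short axis.

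*One target node:*
- 30 x 20 to 22 x 13. Short axis: (13 - 20)/20 = -35.0%, meets the threshold. Longest: (22 - 30)/30 = -26.7%, does not.
- 40 x 20 to 26 x 16. Short axis: (16 - 20)/20 = -20.0%, does not. Longest: (26 - 40)/40 = -35.0%, meets it.

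*One node plus one non-nodal lesion:*
- Node 30 x 20 plus 20, to node 24 x 12 plus 16. Short-axis sum: 40 to 28 = -30%, meets it. Longest-diameter sum: 50 to 40 = -20%, does not.
- Node 36 x 18 plus 20, to node 24 x 15 plus 14. Short-axis sum: 38 to 29 = -23.7%, does not. Longest-diameter sum: 56 to 38 = -32.1%, meets it.

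*Mixed reading (baseline by short axis under 10.1.3.1, follow-up by longest diameter under 10.1.3.3):* an unchanged 30 x 20 node plus an unchanged 20 mm lesion goes from 20 + 20 = 40 to 30 + 20 = 50. That is +25% and +10 mm, which meets the irPD size rule (20% and 5 mm) with no growth.

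**3. Which results can move.**
- Primary endpoint in 12.3, complete response rate: unaffected by an irPR/irSD swap, and the irCR node rule is already short axis.
- Futility rule in 12.2: counts PR or CR and names no ir category.
- A disease-control total counting irPR and irSD together: unaffected by a swap. The spurious irPD of the mixed reading would affect it.
- An irRECIST response rate that separates irPR from irSD, and an irRECIST-based duration of response: exposed. Each patient moved is 1/30 = 3.3 percentage points of the planned sample.

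The documents give no share of patients with nodal target lesions, or with resolved or absent non-target disease. The number of patients affected cannot be computed.

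**The case against.** **The plan steers assessors to the right practice.** Section 10.1.2.1 has only the short axis of a node measured and followed, and 10.1.3.1 brings irRECIST baseline measurement of nodes into line with RECIST 1.1. A site that follows these has no nodal longest diameter to add. Likewise, an assessor who applies the sentence in 10.1.3.2 B reaches the sensible irPR call. This stands: it makes inconsistent classification a risk and not a certainty. It does not remove the contradictory rule from the section that assigns the categories.

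**The single-node examples are artificial, because 3.1.1 requires two sites.** This stands in part. The two-lesion examples flip as well. Criterion 3.1.9 allows a node to be the only measurable site outside the radiation field, and Section 10.1 scores irradiated and unirradiated sites.

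**Stronger readings that the documents do not support.**
- A reader might infer that no enrolled patient can ever be irPR, because irNN means no target disease at baseline and 3.1.6 requires measurable disease. But the irPR row speaks of the status of non-target lesions, and 10.1.3.2 B gives irNN an attainable meaning there. The other entry also breaks off in the text available for this review, so it cannot carry that conclusion.
- A reader might infer that every patient with a 30% fall and no remaining non-target disease is misclassified. Those whose target disease has also gone, with no new lesions, are irCR.
- A reader might infer that a comparison of RECIST with irRECIST is made uninterpretable. Section 12 plans no such comparison; Section 10.1 says only that both criteria are used to score response.

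**Conclusion.** Wrong as written, and it should be corrected. Two contradictions stand: the irPR row against 10.1.3.2 B on non-target lesions, and the longest-diameter sum against 10.1.2.1 and 10.1.3.1 on nodes. The double meaning of irNN adds to the first. The patient with residual target disease and cleared non-target disease is the firm case; the patient who never had non-target disease is affected only on a literal reading.

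The reach is limited to irRECIST results that distinguish irPR from irSD and to irRECIST-based duration of response, with apparent irPD possible only if baseline and follow-up use different axes. The lesion sizes show that crossings can occur in both directions; they say nothing about how often.

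**What to change.** Three wording changes in Section 10.1.3.3:

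1. Define SumD and TMTB, at baseline and at every follow-up, as a sum that takes the longest diameter of each non-nodal lesion and the short axis of each node.
2. Define irPR as a TMTB decrease from baseline of 30% or more, irCR not met, and unequivocal progression in neither the non-target nor the new non-measurable lesions. State that a non-target status of CR, Non-CR/Non-PD or none at baseline is allowed.
3. Give irNN a single meaning. If a label is needed for patients without target disease at baseline, use a separate one.

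Align the tumour-assessment CRF so that it records one nodal axis. The cost is this text and the CRF; no new scans or patients are needed.

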10.1.4 Measurement Time Points

Tumor measurements will be taken and RECIST v1.1/irRECIST will be calculated from the scans (CT, PET CT or MRI brain, chest, abdomen, pelvis, to be determined by the attending physician) performed at baseline, end of treatment visit, and follow up visits.

10.2 Exploratory Outcome

10.2.1 Relevant Subset

All patients are in a single arm.

10.2.2 Measurement Definition

If funding is available, the exploratory outcomes will be assessed. A variety of optional immune response assays will be performed that include Luminex for 51 cytokines testing in serum or plasma, ELISA for MHC class 1 polypeptide-related sequence A (MYCA) and MHC class 1 polypeptide-related sequence B (MYCB) in serum or plasma, immunophenotyping including myeloid-derived suppressor cells (MDSC) and gamma/delta T cells, mass cytometry or CyTOF ICS with phorbol 12-myristate 13-acetate (PMA) + ionomycin stimulation (global immunocompetence assay). Optional tumor biopsies may also be collected to assess response to therapy and changes in immune cell subsets. Optional assays to assess mutational burden/MSI and to measure polyomavirus in the blood may be performed dependent upon funding.

10.2.3 Measurement Methods

At each blood collection, 3 or 4 of 10cc heparin (green-top) tubes for PBMC will be used for intracellular cytokine staining (ICS), immunophenotyping and CyTOF assays, and 1 of 5cc SST (red-top) tube for serum will be used for Luminex and MYCA/MYCB assays. A minimum blood volume of 5ml per tube for the 10cc heparin tubes and 2.5ml per tube for the 5cc SST tube are acceptable for assays.

10.2.4 Measurement Time Points

The optional immune response testing will be performed at baseline, 2 weeks (± 1 weeks) and 8 weeks (± 1 weeks) after radiation therapy. Possible tumor biopsies (optional) may be performed before, during/after treatment to assess response to therapy and changes in immune cell subsets. Optional tests to assess polyomavirus in the blood may be performed at baseline and 3 months ± 1 month.

11. REGULATORY CONSIDERATIONS

11.1 Institutional Review of Protocol

The protocol, the proposed informed consent and all forms of participant information related to the study (e.g. advertisements used to recruit participants) will be reviewed and approved by the Stanford IRB and Stanford Cancer Institute Scientific Review Committee (SRC). Any changes made to the protocol will be submitted as a modification and will be approved by the IRB prior to implementation. The Protocol Director will disseminate the protocol amendment information

to all participating investigators.

11.2 Data and Safety Monitoring Plan

The Stanford Cancer Institute Data and Safety Monitoring Committee (DSMC) will be the monitoring entity for this study. The DSMC will audit study-related activities to determine whether the study has been conducted in accordance with the protocol, local standard operating procedures, FDA regulations, and Good Clinical Practice (GCP). This may include review of the following types of documents participating in the study: regulatory binders, case report forms, eligibility checklists, and source documents. In addition, the DSMC will regularly review serious adverse events and protocol deviations associated with the research to ensure the protection of human subjects. Results of the DSMC audit will be communicated to the IRB and the appropriate regulatory authorities at the time of continuing review, or in an expedited fashion, as needed.

11.3 Data Management Plan

The Protocol Director, or his/her designee, will prepare and maintain adequate and accurate participant case histories with observations and data pertinent to the study. Study specific Case Report Forms (CRFs) will document treatment outcomes for data analysis. Case report forms will be developed using the OnCore database system and will be maintained by the CCTO OnCore team. CRFs will be kept in a locked office, only accessible to the research team.”

12. STATISTICAL CONSIDERATIONS

12.1 Statistical Design

This is a single arm non-randomized open trial to determine the response rate for patients who are treated with both pembrolizumab and palliative radiation therapy.

12.1.1 Randomization

There is no randomization, as all patients are in a single arm.

12.2 Interim Analyses

An interim analysis for futility will be performed after 15 patients have completed the treatment phase. A response rate of 20% is expected, so if one or fewer of 15 patients have demonstrated a PR or CR, the study will be stopped for futility.

12.3 Primary Analysis

Primary Endpoint: The determination of the complete response rate and the 95%CI using Wilson’s method

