1. OBJECTIVES

1.1. Primary Objective

The primary objectives of this study are to assess 1) the safety and 2) efficacy of combining Anti-PD-1/PD-L1 blockade with palliative radiation therapy in patients with Stage IV Merkel Cell Carcinoma. Efficacy for the primary objective will be tumor response rates (CR, PR, SD, irCR, irPR, irSD) at both irradiated and unirradiated sites.

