1.2. Secondary Objectives

Assessment of Overall Survival and disease control rate/duration of response (CR, PR, SD, irCR, irPR, irSD)

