10. MEASUREMENTS

Title: Tumor response rates (CR, PR, SD, irCR, irPR, irSD) as accessed by RECIST v1.1/irRECIST at both irradiated and unirradiated sites

Time Frame: Response will be accessed at the end of treatment visit and follow up visits

Safety Issue: This outcome is not measuring a safety issue. Safety will be monitored using AE assessment during the trial using the CTCAE v5.0 criteria.

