10.1 Primary and Secondary Outcome measures

The primary and secondary outcomes will be assessed by obtaining relevant tumor images at baseline line, end of treatment visit, and then at least every 3 months (± 1 month) for two years and then every 6 months (± 1 month) for years 3-4, then again at year 5 (± 1 month) from the last dose of pembrolizumab or until disease progression. Response and progression will be evaluated using the new international criteria proposed by the revised Response Evaluation Criteria in Solid Tumors (RECIST) guideline (version 1.1)¹¹ as well as the Immune-related RECIST (irRECIST).¹² Changes in the largest diameter (unidimensional measurement) of the tumor lesions and the shortest diameter in the case of malignant lymph nodes are used in the RECIST criteria. RECIST/irRECIST criteria will be used to score response of both the irradiated and unirradiated disease sites.

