10.1.2.5 Best Overall Confirmed Response

Confirmation of CR and PR for determination of best overall response is required for studies with a primary endpoint that includes response.

Time Point Response First time	Time Point Response Subsequent time point ≥ 4 weeks from first time point	BEST overall confirmed response
C	CR	CR
C	PR	SD, PD or PR*
C R	SD	SD provided minimum criteria for SD duration met, otherwise, PD
C R	PD	SD provided minimum criteria for SD duration met, otherwise, PD
C R	NE	SD provided minimum criteria for SD duration met, otherwise, PD
P	CR	PR
P	PR	PR
P	SD	SD
P R	PD	SD provided minimum criteria for SD duration met, otherwise, PD
P R	NE	SD provided minimum criteria for SD duration met, otherwise, NE
N	NE	NE

*If a CR is *truly* met at first time point, then any disease seen at a subsequent time point, even disease meeting PR criteria relative to baseline, makes the disease PD at that point (since disease must have reappeared after CR). However, sometimes ‘CR’ may be claimed when subsequent scans suggest small lesions were likely still present and in fact the patient had PR or SD, not CR at the first time point. Under these circumstances, the original CR should be changed to PR or SD and the best response is PR or SD. PR as best overall response requires ≥ 4 weeks confirmation.

Patients with a global deterioration of health status requiring discontinuation of treatment or die without objective evidence of disease progression at that time should be reported to be off study treatment due to “symptomatic deterioration.” Every effort should be made to document the objective progression even after discontinuation of

treatment.

10.1.2.6 Duration of Response:

Duration of overall response: The duration of overall response is measured from the time measurement criteria are met for CR or PR (whichever is first recorded) until the first date that recurrent or progressive disease is objectively documented (taking as reference for progressive disease the smallest measurements recorded since the treatment started).

The duration of overall CR is measured from the time measurement criteria are first met for CR until the first date that progressive disease is objectively documented.

Duration of stable disease: Stable disease is measured from the start of the treatment until the criteria for progression are met, taking as reference the smallest measurements recorded since the treatment started, including the baseline measurements.

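### The primary efficacy endpoint is contradictory: 1.1 lists response rates down to stable disease, 12.3 names complete response, 12.4 makes response rate secondary, and the 20% in 12.5 has no endpoint attached

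*Combined protocol and SAP*

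**What the plan says.** The combined protocol and SAP describes the efficacy endpoint in several places:

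- **Synopsis and 1.1 (primary objective):** "Efficacy for the primary objective will be tumor response rates (CR, PR, SD, irCR, irPR, irSD) at both irradiated and unirradiated sites", worded identically in the two places.
- **1.2, where the secondary aims are set out:** the text reads "Assessment of Overall Survival and disease control rate/duration of response (CR, PR, SD, irCR, irPR, irSD", which is the same category list, here attached to disease control rate and duration of response.
- **10 (Measurements), outcome title:** "Tumor response rates (CR, PR, SD, irCR, irPR, irSD) as accessed by RECIST v1.1/irRECIST at both irradiated and unirradiated sites". The title itself does not use the word primary.
- **10.1:** "RECIST/irRECIST criteria will be used to score response of both the irradiated and unirradiated disease sites". Neither set of criteria and neither site group is ranked above the other.
- **10.1.2.5:** "Confirmation of CR and PR for determination of best overall response is required for studies with a primary endpoint that includes response".
- **12.1:** the trial is "to determine the response rate for patients who are treated with both pembrolizumab and palliative radiation therapy"; the categories that count as response are not given.
- **12.2 (futility look):** "A response rate of 20% is expected, so if one or fewer of 15 patients have demonstrated a PR or CR", the study stops.
- **12.3 (primary endpoint):** "The determination of the complete response rate and the 95%CI", by Wilson's method.
- **12.4:** response rate appears among the secondary endpoints, with overall survival and duration of response.
- **12.5:** 30 patients, 87% probability of a Wilson half-width of 15.5% at a rate of 20%, and an interval of [9.5%, 37.3%] if exactly 20% is observed. The endpoint is not named.

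Sections 12.3.2 and 12.4.2 plan descriptive summaries with Wilson intervals. No null rate or success threshold is given for the final analysis.

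**The concern.** Section 12.3 and the primary objective cannot both define the primary efficacy result. If the list in 1.1 is one pooled rate, 12.3 contradicts it. If it is a list of separate rates, 12.3 selects one and no section explains the choice. The response rate that 12.1 calls the aim becomes secondary in 12.4, and 1.2 gives the category list of the primary objective to a secondary objective.

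Two things are at stake. First, the final analysis is purely descriptive, so the reported rate and its interval are the whole primary efficacy result. A plan that supports several different rates as primary leaves that choice open until the data are known. Second, the justification for 30 patients rests on a 20% that 12.5 ties to no endpoint, so a reader cannot tell whether the stated precision belongs to the endpoint named in 12.3.

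**Working it through.** **1. The labels side by side**

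| Section | Measure | Status |
|---|---|---|
| Synopsis, 1.1 | CR, PR, SD and immune-related counterparts, two site groups | primary |
| 10 | same list | outcome title, status not stated |
| 1.2 | disease control rate/duration of response, same list | secondary |
| 12.1 | response rate, categories not stated | aim of the trial |
| 12.2 | PR or CR, 20% expected | futility look |
| 12.3 | complete response rate | primary |
| 12.4 | response rate | secondary |
| 12.5 | rate of 20%, endpoint not stated | basis for N=30 |

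Choosing the categories does not finish the definition. Three cumulative choices (CR, CR+PR, CR+PR+SD), two sets of criteria and two site groups give 3 × 2 × 2 = 12 candidate rates, before a patient-level overall response is added.

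**2. Reproducing 12.5**

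Inputs from 12.5: n = 30, rate 20%, half-width 15.5%, 95% Wilson interval (z = 1.96, z² = 3.84). For x responders and p = x/n:

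- centre = (p + z²/2n) / (1 + z²/n)
- half-width = z × √(p(1−p)/n + z²/4n²) / (1 + z²/n)

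At x = 6, p = 0.20: centre = (0.20 + 0.0640)/1.1280 = 0.2341, and half-width = 1.96 × √(0.005333 + 0.001067)/1.1280 = 0.1390. The interval is [9.5%, 37.3%], as stated.

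The half-width is 15.13% at x = 8 and 15.61% at x = 9. By symmetry, it is therefore 15.5% or less when x ≤ 8 or x ≥ 22. With X ~ Bin(30, 0.20), P(X ≤ 8) = 0.8713 and the upper tail is negligible. This matches the stated 87%. There is no arithmetic error.

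**3. How far the 87% depends on the endpoint**

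The same calculation at the rates in section 2.2, with 30 analysed:

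| Background rate | Value | P(half-width ≤ 15.5%) |
|---|---|---|
| Avelumab CR | 11.4% | 99.5% |
| Value in 12.5 | 20% | 87.1% |
| Pembrolizumab CR | 24% | 71.9% |
| Avelumab overall response | 33% | 29.9% |
| Pembrolizumab overall response | 56% | 4.1% |

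These rates are illustrative only. The pembrolizumab figures come from treatment-naive patients, whereas this trial also takes patients after prior therapy (2.4), including prior anti-PD-1/PD-L1 (4.1.1), and adds radiation.

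**4. Spread of possible headline results**

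Pembrolizumab background rates applied to 30 patients:

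- CR: 0.24 × 30 = 7.2, so 7/30 = 23%, Wilson [11.8%, 40.9%]
- CR+PR: 0.56 × 30 = 16.8, so 17/30 = 57%, [39.2%, 72.6%]
- CR+PR+SD: (0.56 + 0.10) × 30 = 19.8, so 20/30 = 67%, [48.8%, 80.8%]

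The lowest and highest differ by 13 of 30 patients, or 43 percentage points.

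**5. Worst-case precision**

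The Wilson half-width is largest near x = n/2: 16.85% with 30 analysed (x = 15), 17.1% with 29 and 17.6% with 27. Fewer than 30 matters because 12.3.1 counts only patients who received pembrolizumab and completed their radiation course.

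**The case against.** The strongest defence is that little turns on the label. There is no hypothesis test, CR rate and response rate are both named endpoints, and both would be reported with Wilson intervals. A futility look may properly use a different endpoint from the primary. Complete response rate in 12.3 might also be loose wording for overall response rate.

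Part of this stands. No pass/fail decision is affected, and the risk is selective emphasis rather than a suppressed result. The loose-wording reading is weak, because 12.4 lists response rate separately as secondary. Reporting several rates does not settle which one is the primary result.

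A reader might infer more than the documents support, in three ways:

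- *That 12.5 sizes the trial on a secondary endpoint.* This follows only if its 20% means CR+PR. Section 12.2 points that way, but it concerns the interim look. The background CR rates of 11.4% and 24% bracket 20%, while the background overall response rates of 33% and 56% lie well above it. The meaning cannot be determined from the text.
- *That the futility rule would often stop the trial if applied to CR.* Section 12.2 explicitly counts PR or CR; a CR-only rule is not in the plan.
- *That section 10 is a further place that labels the list primary.* Its outcome title does not say so; the label comes from the synopsis and 1.1.

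**Conclusion.** The contradiction is real, and it concerns the trial's main efficacy result. The synopsis and 1.1 conflict with 12.3, while 12.1 and 1.2 do not fit with 12.4 and 1.1. It should be resolved before efficacy data are analysed.

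Whether the stated precision describes the 12.3 endpoint cannot be determined. If the 20% is CR+PR, as in 12.2, the CR rate in 12.3 has no planning value. If it is CR, the 12.5 figure does not describe the CR+PR response rate. Either way the 87% holds only for an endpoint with a rate near 20%; across the background rates the corresponding probability runs from 4.1% to 99.5%.

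This does not show that the trial is too small or that 12.5 is miscalculated. The harm is a headline that can be picked after the fact, illustrated by 23%, 57% or 67% from the same 30 patients. Those figures assume the background rates carry over to a different population and 30 patients analysed; the conflict in the wording needs neither assumption.

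**What to change.** Name one primary efficacy endpoint by its response categories, by RECIST v1.1 or irRECIST, and by site group (irradiated, unirradiated or overall), with the confirmation that 10.1.2.5 already requires. CR+PR is one option and agrees with 12.2; the choice is the sponsor's.

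Then:

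- Use that endpoint consistently in the synopsis, 1.1, 1.2, 10, 12.1, 12.3, 12.4 and 12.5, and list the other rates as secondary. Sections 1.2 and 12.4 must be included, or the contradiction remains.
- State which endpoint the 20% refers to in 12.2 and in 12.5. If 12.2 keeps a different endpoint from the primary, say so.
- Restate the 12.5 precision at the expected rate of the chosen endpoint, and give the values for fewer than 30 analysed.

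The cost is wording and one recalculation. N=30 can stay, since the half-width cannot exceed 16.85% with 30 analysed. The downside is that the stated precision may look less favourable if the chosen endpoint is expected above 20%.
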